The patients' data on the three measures were recorded within the Excel Workbooks under three tabs representing the first, second, and third clinical observation periods. So each tab recorded three measures. The first and last tabs recorded probing depth, gingival index, and plaque. The second visit included only gingival index and plaque. Each patient had an individual Excel Workbook. Data were sorted into analysis format through two Excel macros that created a single master data for global scores and a single one for implant and non-implant scores. Data files were saved in comma separated value (csv) format in both wide and long formats for R and SPSS data management, inspection, cleaning, and analyses.

Since many individual variable distributions varied substantially from normal, a gamma log-link function was applied to reduce bias in most statistical tests.

Label Key and Lot #s for Peri-Implant Mucositis Study with Stony Brook University

Rowpar Pharmaceuticals, Inc., released the test material label codes after completion of the clinical study and statistical analysis of the data. The products were labelled as follows:

Study Number: SBU-RPR-Peri-Implant Mucositis-2018

Oral Rinse A: ClōSYS Placebo Oral Rinse, Lot #: 2-80516

Oral Rinse X: ClōSYS® Ultra Sensitive (Unflavored) Oral Rinse, Lot #: 8122A 14-80430

Results

Patients

Fifty-two percent (29/56) of patients in both groups had only one implant. Patients in the control group (Group A) had a total of 47 implants: 11 patients had just one implant, 13 had 2, 2 had 3, and 1 had 4 implants. In the test group (Group X), there were 42 total implants in 26 patients: 18 had 1 implant, 9 had 2, and 2 had 3 implants (see Figure 1). Table 1 gives average values (and standard error of the mean) of Gingivitis Index, Plaque score, and Probing depth at baseline.

Figure 1. Bar chart of numbers of implants per person in control group (Group A) and test group (Group X).

[figure not shown]

Table 1. Patient dental measures at baseline.

		n of patients	n of implants	Modified Gingivitis Index (MGI) (sem)	Plaque score (PS) (sem)	Probing Depth mean (sem)
Control Group (Group A)	implants	27	47	2.06 (0.048)	2.77 (0.115)	3.40 (0.109)

	non-implanted teeth			1.87 (0.039)	2.32 (0.101)	2.72 (0.099)
Test Group (Group X)	implants	26	39	2.82 (0.049)	2.84 (0.057)	2.447 (0.080)
	non-implanted teeth			2.01 (0.028)	2.99 (0.078)	2.65 (0.079)

Global Score Analyses

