From raw data of individual teeth, each patient received a global index of periodontal disease, gingival index, and plaque for each visit. The global index for each of these measurements was found by dividing the sums of patient probing depth, gingival index, and plaque findings collected for each tooth by the number of teeth assessed. Over the three assessment periods, global scores of probing depth, gingival index, and plaque were collected for the first and last visits with probing depth scores not collected during the second visit. These outcomes are measured as individual slopes of responses across the three observation visits. The slope represents the rate of change.

The overall view of the response of each measure to the treatment group is summarized in the following general linear model Table 2. Table 3 shows the cell statistics for the slopes of each condition and outcomes reported in Table 2.

Table 2. Master table of variance components attributable to treatment on individual rates of change on the three measures: probing depth, gingival index, and plaque.

Source	Variable	Type III SS	df	MS	F	Sig.
Group	Slope of probing depth, time 1 to 3	0.125	1	0.125	1.191	0.28
	Slope of gingivitis index, time 1 to 3	0.485	1	0.485	11.748	0.001
	Slope of plaque score, time 1 to 3	4.019	1	4.019	69.751	0.000
Error	Slope of probing depth, time 1 to 3	5.75	55	0.105		
	Slope of gingivitis index, time 1 to 3	2.27	55	0.041		
	Slope of plaque score, time 1 to 3	3.169	55	0.058		
Total	Slope of probing depth, time 1 to 3	6.519	57			

Slope of gingivitis index, time 1 to 3	6.135	57
Slope of plaque score, time 1 to 3	18.861	57
Corrected Total	Slope of probing depth, time 1 to 3	5.875
	Slope of gingivitis index, time 1 to 3	2.755
	Slope of plaque score, time 1 to 3	7.187
	R Squared = .021 (Adjusted R Squared = .003)	
	R Squared = .176 (Adjusted R Squared = .161)	
	R Squared = .559 (Adjusted R Squared = .551)	

Table 3. Details of cell statistics for analysis described in Table 2.

Descriptive Statistics					
	N	Minimum	Maximum	Mean	Std. Deviation
Probing depth at time 1	57	2.04	4.63	2.71614	0.432843
Probing depth at time 3	57	0	4.42	2.50351	0.804056
Gingivitis index at time 1	57	1.41	2.23	1.97158	0.172065
Gingivitis index at time 2	57	0	2	1.71754	0.364095
Gingivitis index at time 3	57	0	1.92	1.48456	0.451688
Plaque score at time 1	57	1.47	3.54	2.67895	0.555475
Plaque score at time 2	57	0	3.11	2.19614	0.596444
Plaque score at time 3	57	0	2.92	1.77386	0.618124

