Slope of probing depth, time 1 to 3	57	-1.47	0.015	-0.10632	0.323886
Slope of gingivitis index, time 1 to 3	57	-0.99	-0.03	-0.24351	0.221807
Slope of plaque score, time 1 to 3	57	-1.53	-0.045	-0.45254	0.358255
Valid N (listwise)	57				

Global Probing Depths (GPD)

Global probing depth (GPD) collected at the first visit did not differ significantly between groups; control group's (Group A) initial GPD was 2.76 (SEM = 0.092) interval, and 2.68 (0.071) for test group (Group X), a non-significant statistical difference ($p = 0.48$).

Neither did the GPD score differ between final visits of control group (Group A) (GPD = 2.64 (0.130) and test group (Group X) (GPDI = 2.37, (0.166), $t = 1.27$, $df = 55$, $p = 0.28$. Nonetheless, the GPD decreased significantly for control group (Group A), ($p = 0.028$; for X, $p < 0.001$) for both groups, but the group decreases were not significantly different from each other. Both mouthwashes reduced probing depth similarly.

The key signal of treatment effectiveness is a statistically significant treatment-by-time interaction, where improvement over time is greater for one treatment than another. Nearly parallel lines in Figure 2 and statistical testing indicated no appreciable and significant treatment-by-time interaction for GPD (See Figure 2, Figure 3).

Figure 2. Interaction plot showing that group assignment did not interact with time for probing depth.

[figure not shown]

Figure 3. Boxplots of probing depth results from treatment by control group (Group A) and test group (Group X). Probing depth was not affected differentially by the mouthwash treatments. Both conditions reduced probing depth slightly but not statistically significant.

Global Plaque Score

Control group (Group A) and test group (Group X) differed significantly in global plaque score (GPS) at initial assessment, requiring an additional analysis of covariance to confirm that a significant time by treatment interaction was not an artifact from the initial difference in GPS (See interaction plot, Figure 4, detailed in Figure 5). The test group's (Group X) initial average GPS was 3.00 (SEM = 0.071) versus 2.35 (0.097) for the control group (Group A), a significant difference ($t = -5.45$, $df = 50$, $p < 0.001$). At assessment 3, the last observation, the test group's (Group X) GPS (1.57, SEM = 0.110) was significantly lower than that for the control group (Group A); GPS = 1.98 (0.110), $t = 2.633$, $df = 55$, $p = 0.011$.

[figure not shown]

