Figure 4. Interaction plot showing that group assignment interacted with time on the measure plaque.

[figure not shown]

Figure 5. Boxplots of plaque measures comparing treatment control group (Group A) and test group (Group X) for GPS. Test group (Group X) started with higher levels of plaque. Plaque decreased more in the test group (Group X) than in the control group (Group A), though both decreased significantly.

An analysis of covariance (ANCOVA) with the first visit as covariate was used to statistically control for the difference in average plaque scores at intake. ANCOVA results confirmed that test group (Group X) produced a significantly lower GPS measures (ANCOVA $F = 34.82$, $df = 1$, $p < 0.0001$), even with significant differences in the initial scores.

To further explore and confirm control rinse (rinse A) and test rinse (rinse X) treatment effects on plaque measurement, from Time 1 to Time 3, both a Student's t-test and a Bayesian analysis of group means were employed. The Bayesian analysis supported the ANCOVA results.

Another t-test showed test group's (Group X) GPS absolute change and rate of change were significantly greater than for control group (Group A): -1.43 versus 0.365, respectively. This difference is considered a large effect size, Cohen's $d = 2.21$ ($t = 8.35$, $df = 1$, $p < 0.0001$). Thus, the changes and rates of change for GPS were greater for the test group (Group X) than the control group (Group A).

Global Gingival Index Score

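### Follow-up zeros, very probably unobserved visits, are analysed as real scores in Tables 2–3 and in the global tests that use the same 57 values

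*Combined protocol and SAP*

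**What the plan says.** Each global score is a patient's tooth scores summed and divided by the number of teeth measured ([11], Outcomes). Eligibility requires at least 20 natural teeth ([8]).

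Table 3 reports N, minimum, maximum, mean and SD. At the last visit it gives "Probing depth at time 3 57 0 4.42 2.50351 0.804056" and "Gingivitis index at time 3 57 0 1.92 1.48456 0.451688". Plaque at time 3, and MGI and plaque at time 2, also have minimum 0. The baseline minima are 2.04 (probing depth), 1.41 (MGI) and 1.47 (plaque). Listwise N is 57.

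Table 2 tests the arms on individual slopes with 55 error df. Table 3 summarises the probing-depth slope as "Slope of probing depth, time 1 to 3 57 -1.47 0.015 -0.10632 0.323886". Other global tests carry the same df or the same statistic: final probing depth (df 55), final plaque ("GPS = 1.98 (0.110), $t = 2.633$, $df = 55$, $p = 0.011") and plaque change ("d = 2.21$ ($t = 8.35$, $df = 1$, $p < 0.0001").

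On probing depth, the text says "the GPD decreased significantly for control group (Group A" and likewise for the test arm, while the Figure 3 caption says "Both conditions reduced probing depth slightly but not statistically significant".

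Patient counts differ. The synopsis has 54 randomised, Table 3 has 57, Results (Patients) uses a denominator of 56, and Table 1 has 27 control and 26 test patients. For the test arm the text gives "42 total implants in 26 patients: 18 had 1 implant, 9 had 2, and 2 had 3 implants", which sums to 29 patients.

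The documents report no withdrawal or missed visit and give no missing-data rule. They say that a gamma model with log link was used for most tests.

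**The concern.** An MGI or plaque score of 0 is conceivable. A whole-mouth mean probing depth of exactly 0 is not, and the zeros appear in all three indices at once. If they stand for visits that were not made, the analysis scores an unmeasured patient as completely healed. If that happened more often in the test arm, it favours the test rinse.

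What is at stake is the size of the global probing-depth fall and the Table 2 arm difference on MGI, the stated primary outcome. The Conclusions also cite slopes as evidence that the effect is robust to the baseline imbalance, and the reported slope tests contain the zeros. A gamma model is not defined at 0, so these patients must have been handled in some unreported way wherever that model was fitted.

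**Working it through.** **1. Reproduce Table 2 from Table 3.** Slope = (time 3 − time 1)/2; corrected SS = 56 × SD².

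- Mean slopes: probing depth (2.50351 − 2.71614)/2 = −0.1063; MGI (1.48456 − 1.97158)/2 = −0.2435; plaque (1.77386 − 2.67895)/2 = −0.4525. All match Table 3.
- Corrected SS: 56 × 0.323886² = 5.875; 56 × 0.221807² = 2.755; 56 × 0.358255² = 7.187. All match Table 2.
- MGI: F = 0.485/(2.27/55) = 11.75 (printed 11.748), p = 0.0012. The Conclusions state P < 0.001 for both gingivitis and plaque.
- √69.751 = 8.35, the t printed for plaque change.

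So the time-3 zeros are inside Table 2 and the plaque-change test.

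**2. Arm sizes within the 57.** From the baseline plaque means, control n = 57 × (3.00 − 2.67895)/(3.00 − 2.35) = 28.2, or 27.7–28.6 allowing for rounding. The arms are therefore 28 and 29. Check: 8.35 × √(1/28 + 1/29) = 2.21, the printed d; arms of 27/26 would give 2.29.

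**3. How many zeros?** With k zeros removed from n values, the mean becomes n × mean/(n − k). The residual SS is (n − 1)SD² + n × mean² − (n − k) × (new mean)². A negative residual SS rules k out.

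| Pooled | SD, k=2 | k=3 | k=4 | k=5 | Baseline SD |
|---|---|---|---|---|---|
| MGI, time 3 | 0.36 | 0.29 | 0.19 | impossible | 0.17 |
| Probing depth, time 3 | 0.66 | 0.56 | 0.42 | 0.19 | 0.43 |
| MGI, time 2 | 0.16 | impossible | – | – | 0.17 |

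By arm at time 3, with SD = SEM × √n:

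- Control probing depth, 2.64 (0.130), n = 28: k=1 gives mean 2.74, SD 0.46 (baseline 0.49); k=2 is impossible.
- Test probing depth, 2.37 (0.166), n = 29: k=3 gives mean 2.64, SD 0.38 (baseline 0.38); k=4 is impossible.

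Four zeros can therefore only be 1 control and 3 test. That leaves 27/26, the Table 1 arms, and 53 patients, which fits the 102 error df of the implant models (2 × 53 − 4). The itemised test arm has 29 patients and 42 implants against 26 and 39 in Table 1, again three patients. The control zero has no such counterpart, because the text itemises 27.

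**4. Effect of removing 1/3 zeros.** A patient who falls to 0 has slope −baseline/2. The baseline of a zero patient is therefore at most twice the size of the minimum slope (MGI 1.98, probing depth 2.94, plaque 3.06) and at least the Table 3 baseline minimum. The ranges below cover all sets within these limits that agree with the baseline SEMs and the Table 2 error SS.

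- *MGI.* Slope difference = √(0.485 × 57/(28 × 29)) = 0.1845, so the difference in change is 0.369 (control −0.299, test −0.668). With every zero patient's baseline at 1.98: control (28 × −0.299 + 1.98)/27 = −0.237; test (29 × −0.668 + 3 × 1.98)/26 = −0.517; difference 0.28. Full range 0.26–0.32, so 0.37 is overstated by about 15–42%. F is at least 12.9.
- *Probing depth.* Summed change = 57 × −0.2126 = −12.12 mm. With four baselines of 2.04 the mean of the rest is (−12.12 + 8.16)/53 = −0.075. Full range −0.037 to −0.075 against −0.213, so the zeros make 67–84% of the summed fall. By arm: control 0.12 becomes 0.01–0.05; test 0.30 becomes 0.03–0.10. The Day-90 difference of 0.27 becomes 2.74 − 2.64, about 0.09 (0.08–0.11 with rounding).
- *Plaque.* Day-90 means become 2.05 and 1.75. The difference goes from 0.41 to 0.30 (0.29–0.31), and t from 2.6 to about 3.0–3.1. The arm difference in change goes from 1.06 to 0.92–1.11, with F about 70 or more.

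**The case against.** The strongest case against accepts the zeros but disputes their number and their importance.

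- **The count is inferred.** Strict arithmetic only caps the zeros at one in control and three in test; choosing four rests on SDs returning to near baseline. With other splits (control/test), the MGI difference after removal would be 0.31–0.38 (1/2), 0.36–0.40 (1/1) or 0.41–0.43 (1/0), so it might not shrink. Two zeros would explain only 41–49% of the probing-depth fall. This stands as a limit, and the sizes given here are conditional on 1/3. That split is nevertheless well supported: both pooled SDs and both arm SDs return to near baseline, and the remaining 27/26 matches Table 1.
- **The corroboration is imperfect.** Table 1 is a baseline table, so it does not directly count Day-90 observations. The d of 2.21 would also fit arms of 27/30. Both points are right; the baseline plaque means, not d, fix 28/29.
- **The stated MGI effects are not shown to be inflated.** The report prints reductions of 27.3% and 20.4%, not a difference of 0.37, and the MGI ANCOVA has df 51. This is fair. The percentages match neither the zero-coded data (33%/16%) nor the data without zeros (about 25–27%/12–13%), so their source is unknown.
- **The within-arm probing-depth p-values (0.028 and < 0.001) probably come from elsewhere.** With 1/3 zeros in the data and zero-patient baselines of at least 2.04, a paired t-test gives at best about 0.11 and 0.011. This stands, and it is a further reason to re-test that statement.
- **Significance survives.** Agreed for MGI and plaque, probably. It does not make the effect sizes in the master tables right.

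**Conclusion.** The concern holds and should be corrected before the global results are relied on. That Tables 2–3 contain values which cannot all be measurements, and that Table 2 tests them, follows directly from the printed figures. That the zeros are unobserved visits is a strong inference. Their number and split (1 control, 3 test) are back-calculated, assuming arms of 28/29.

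On that basis most of the reported global probing-depth fall is an artefact of the zeros, and the Table 2 MGI difference is overstated by about 15–42%. The Day-90 plaque difference is overstated by about 0.1, and the plaque-change difference could move either way. Whether the remaining probing-depth fall is significant cannot be settled from the published figures (t from about −1.4 to much larger in size).

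Baseline comparisons and the 53-patient implant models are not affected. The MGI ANCOVA and the 27.3%/20.4% reductions are not shown to be affected.

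**What to change.** 1. Trace each zero to its source record and set unobserved visits to missing.
2. Re-run Tables 2–3, the global t-tests on 55 df, the plaque-change t and d, and any ANCOVA, Bayesian or repeated-measures analysis that used the zeros.
3. State the missing-data method, for example a likelihood-based mixed model on all randomised patients, and add a sensitivity analysis. State how the gamma log-link fits handled these patients.
4. Report missing visits by arm and visit, and reconcile 57, 56 and 53 with the 54 randomised.
5. Re-test the within-arm probing-depth statement and reconcile it with the Figure 3 caption. Reconcile the 27.3%/20.4% MGI reductions with Tables 2–3, and the P < 0.001 in the Conclusions with Table 2.

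The cost is checking about four Day-90 and two Day-14 records, re-running existing analyses and correcting the report. No new data are needed. If the 1/3 split is confirmed, the probing-depth fall, the MGI arm difference and the Day-90 plaque difference will be smaller.

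### Similar probing-depth reduction is concluded from a non-significant test with no margin or interval, and the final-visit p-value beside it should be 0.21, not 0.28

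*Combined protocol and SAP*

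**What the plan says.** Section 11 (Statistical Evaluation) first ties the primary objective to the gingival index (MGI) alone. It then lists probing depth, gingival index and plaque as three primary outcomes, to be tested through the treatment-by-time interaction. That is a test of difference. No equivalence margin is set for any outcome.

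The Global Probing Depths section of the Results gives these figures:

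- Baseline: "control group's (Group A) initial GPD was 2.76 (SEM = 0.092) interval", and "2.68 (0.071) for test group (Group X), a non-significant statistical difference ($p = 0.48".
- Final visit: "Neither did the GPD score differ between final visits of control group (Group A) (GPD = 2.64 (0.130" in control; in test, "GPDI = 2.37, (0.166), $t = 1.27$, $df = 55$, $p = 0.28".
- Within-arm falls: p = 0.028 (control) and p < 0.001 (test). The two falls are described as not significantly different from each other.

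It then concludes "Both mouthwashes reduced probing depth similarly". The next paragraph says that near-parallel lines in Figure 2, together with statistical testing, "indicated no appreciable and significant treatment-by-time interaction for GPD".

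Table 2, in the row "Slope of probing depth, time 1 to 3", reports the between-group test as F = 1.191 with p = 0.28.

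**The concern.** Failure to reject a null hypothesis of no difference is not evidence of a like effect. To say that two rinses acted similarly, one needs a stated margin, or at least an interval narrow enough to exclude differences that matter. The section has neither, and the printed means do not look alike on their face.

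The p-value printed with the final-visit comparison also does not follow from its own t and degrees of freedom, and it equals the p-value of another test in Table 2.

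At stake is what may be said about probing depth, which one of the two statements in Section 11 makes a primary outcome, and the accuracy of one reported result.

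**Working it through.** **1. Table 2 slope test (reproduces).** Inputs: group SS 0.125, error SS 5.75, error df 55.

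- Error MS = 5.75/55 = 0.1045.
- F = 0.125/0.1045 = 1.196, against 1.191 printed; the gap is rounding of the sums of squares.
- For F = 1.191 on 1 and 55 df, p = 0.280. The printed 0.28 is right for this test.

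**2. Final-visit comparison (does not reproduce).** Inputs: 2.64 (SEM 0.130) and 2.37 (SEM 0.166).

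- Difference = 0.27; SE = sqrt(0.130² + 0.166²) = 0.211; t = 0.27/0.211 = 1.28. The printed t of 1.27 is sound.
- Two-sided p for t = 1.27 on 55 df = 0.209 (0.208 to 0.211 over the rounding of t).
- Variants: one-sided 0.105; normal 0.204; Welch 0.210; pooled variance 0.204 to 0.213 over several arm splits; extreme rounding of means and SEMs 0.19 to 0.22. None gives 0.28.
- p = 0.28 would need t of about 1.09, and sqrt(1.191) = 1.09. The printed value is therefore that of the slope test in step 1.

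**3. Change in each arm, as tabulated.**

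- Control: 2.76 - 2.64 = 0.12 mm (0.12/2.76 = 4.3%).
- Test: 2.68 - 2.37 = 0.31 mm (0.31/2.68 = 11.6%).

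**4. Interval for the difference in change.** The tabulated slope is half of the first-to-last change: 2 × (-0.10632) = -0.2126, and the Table 3 means give 2.50351 - 2.71614 = -0.2126. Arm sizes within the 57 are not stated, so 28 control and 29 test are assumed.

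- SE of slope difference = sqrt(0.1045 × (1/28 + 1/29)) = 0.0857.
- Slope difference = sqrt(1.191) × 0.0857 = 0.0935.
- Doubled: extra reduction in the test group = 0.187 mm, SE 0.171.
- With t(0.975, 55) = 2.004: 0.187 ± 0.343, so the 95% CI is -0.156 to 0.530 mm.
- Splits of 29/28 and 27/30 give about the same interval (-0.16 to 0.53).

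The interval contains zero. It also contains an advantage for the test rinse larger than the whole change in either arm.

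**5. Quality of the inputs.**

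- Table 3 has N = 57, but 54 patients were randomized.
- The smallest final probing depth in Table 3 is 0, which is implausible as a whole-mouth mean in patients required to have at least 20 natural teeth.
- The lowest slope, -1.47, is a fall of 2.94 mm. That one record contributes 1.47² = 2.16 of the uncorrected total of 6.519, about a third.

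Zeros standing for missing values would explain this, but the documents do not say so.

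**The case against.** The best defence is that the sentence is shorthand. It directly follows the statement that the falls did not differ significantly, it does not favour the test product, and the Conclusions claim superiority only for plaque and gingival index. Nor does the p-value stand alone: the section also cites near-parallel lines in Figure 2 (not shown in the text available), and the later section on implants and probing depth puts the time-by-group difference at under 1%. It would be wrong to say that the conclusion rests on p = 0.28 only.

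Most of this stands, and it limits the weight of the point. It does not rescue the wording. A plot of means shows no precision. The basis of the figure under 1% is not given, and it sits badly with global falls of 4.3% and 11.6%. The same passage calls that interaction significant and seen before, which contradicts the global section. It relies on Table 5, whose caption says probing depth but whose header says the measure is GGI.

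A second objection is that the interval derived here may itself be an artefact of the zero values. That stands too. It is a reason to clean the data before publishing an interval, and equally a reason not to assert similarity from the same records.

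A reader might also be tempted to cite the ratio 0.31/0.12, about 2.6, as showing that the rinses acted differently. The documents do not support that: the interval includes zero, and the ratio may be driven by a few suspect records.

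**Conclusion.** The concern holds in a limited form. The available analysis shows no difference in probing-depth change; it does not show similarity. As tabulated, the difference is 0.19 mm, 95% CI about -0.16 to 0.53 mm. This assumes a near-equal split of the 57 records, takes the Table 2 error term at face value, and is provisional until the count of 57 and the zero minimum are explained. The word *similarly*, and the description of the interaction as not appreciable, claim more than that.

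The final-visit p-value is 0.21, not 0.28. This needs no assumption beyond the printed t and df. That 0.28 was carried over from the slope test is a probable explanation, not an established one. A reader might infer that the correction changes the result; it does not, since both values are non-significant.

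Nor should the point be put as a false claim on the undisputed primary outcome, because Section 11 gives probing depth that status in one place and names MGI alone in another. Severity is minor: the significance verdict and the main plaque and gingival conclusions are unchanged.

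**What to change.** 1. In the Global Probing Depths section, print the final-visit result as t = 1.27, df = 55, p = 0.21. Keep p = 0.28 for the Table 2 slope test only.
2. Explain the 57 records against 54 randomized and resolve the zero values. Then rerun the probing-depth model and report the arm difference in change with its 95% CI. The interval derived above should not be published as it stands.
3. Replace the two phrases on similarity and on the interaction with a statement that no difference was shown and that equivalence was not tested.
4. Reconcile this with the section on implants and probing depth, which calls the time-by-group interaction significant, and correct or relabel Table 5. Reconcile also the Figure 3 caption, which says that neither reduction was significant, with the within-arm p-values of 0.028 and < 0.001.
5. State once in Section 11 whether probing depth is a primary outcome.

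The cost is a check of the patient workbooks, one rerun of an existing model and a few sentences. No new data are needed. The probing-depth claim becomes weaker.

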Transformed Variable: Average outcomes					
Source	Type III Sum of Squares	df	Mean Square	F	Sig.
Intercept	2790.339	1	2790.339	9371.807	0.000
Implant	2.916	1	2.916	9.793	0.002
Measure	13.625	1	13.625	45.761	0.000
Group	1.954	1	1.954	6.562	0.011
Implant * measure	7.58	1	7.58	25.459	0.000
Implant * group	0.018	1	0.018	0.061	0.805
Measure * group	8.331	1	8.331	27.981	0.000
Implant * measure * group	16.127	1	16.127	54.166	0.000
Error	60.738	204	0.298		

Implants and Probing depth

Probing depth scores (PDS) were only collected at initial and last observations visits 1 and 4. At intake, control group (Group A) patients had significantly higher levels of probing depth around implanted teeth (mean = 2.93, SEM = 0.094) than in non-implanted teeth (2.69, 0.063), with $t = 2.31$, $df = 53$, $p = 0.025$. In addition, control group (Group A) implant site probing depth was greater at intake than for test group (Group X) probing depth at implanted sites, 3.40 (0.109) versus 2.45 (0.080) respectively, with $t = 7.07$, $df = 52$, $p < 0.001$.

[figure not shown]
Table 5 represents the results in an overall test of significance with PDS as a dependent variable. There were two notable interactions. One was a time by group interaction, representing that probing depths changed significantly differently over time. Another was a three-way interaction time-by-implant-by-group assignment. The time-by-group interaction was seen before in the PDS score and while significant, the actual difference was less than 1%. The three-way interaction is a false signal in that implant scores probe scores increased slightly in the test group (Group X) and decreased slightly in the control group (Group A) – and neither change was significant.

Probing depth scores for implant and non-implant sites did not change significantly in both groups did not change significantly in both implant and non-implant sites as observed over time for both groups. Figure 8 illustrates the lack of change in implant and non-implant depth scores in either group.

Table 5. Summary results of general linear model of probing depth measures for implant sites over time.

Tests of Within-Subjects Contrasts					
Measure: GGI					
Source	Type III Sum of Squares	df	Mean Square	F	Sig.
Time	15.113	1	15.113	563.159	0.000
Time * implant	1.507	1	1.507	56.172	0.000
Time * group	0.941	1	0.941	35.047	0.000
Time * implant * group	0.001	1	0.001	0.041	0.840
Error(Time)	2.737	102	0.027		

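### The report says probing depth fell significantly in both arms and also that neither fall was significant, and the stated within-arm p-values are not reproducible by a t-test from the published figures

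*Combined protocol and SAP*

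**What the plan says.** Section 11 (Statistical Evaluation) names gingival inflammation as the measure for the primary objective, then lists probing depth among three primary outcomes.

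Under Global Probing Depths (GPD) the text reads: "Nonetheless, the GPD decreased significantly for control group (Group A), ($p = 0.028$; for X, $p < 0.001$) for both groups". It adds that the decreases did not differ between arms and concludes: "Both mouthwashes reduced probing depth similarly". The Figure 3 caption, on the same global score, says: "Both conditions reduced probing depth slightly but not statistically significant".

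Under Implants and Probing depth, where scores are split by site, the text says depth "did not change significantly in both implant and non-implant sites as observed over time for both groups".

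Table 2 tests only the difference in slopes between arms (F = 1.191, p = 0.28) and contains no within-arm test. Data Management and Statistical Analysis says a gamma log-link was used for most tests. The test behind the two within-arm p-values is not named.

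**The concern.** The GPD text and the Figure 3 caption make opposite statements about one quantity. A reader cannot tell whether the trial found a within-arm fall in an outcome that Section 11 calls primary. Correcting only one of the two would be enough if the other agreed with the published variances, so the p-values need checking.

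The data behind the fall also look doubtful. A whole-mouth mean probing depth of 0 at Day 90 is hard to read as a measurement when no baseline value was below 2.04. If zeros stand for missed visits, they enlarge both the mean fall and its variance.

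**Working it through.** **Inputs.** GPD text: baseline mean (SEM) 2.76 (0.092) control and 2.68 (0.071) test; final 2.64 (0.130) and 2.37 (0.166). Table 2, probing-depth slope: group SS 0.125, error SS 5.75 on 55 df. Table 3: N = 57, mean slope -0.10632, SD 0.323886, slope range -1.47 to 0.015.

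**Reproducing Table 2.** F = 0.125/(5.75/55) = 1.196, p = 0.28, as stated apart from rounding. Corrected total = 56 × 0.323886² = 5.875, as stated. The slope is half the change: (2.50351 - 2.71614)/2 = -0.1063. Table 2 is internally sound for this outcome.

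**Arm slopes.** The arm split of the 57 is not stated. I assume 28 control and 29 test, which fits the Table 3 SD at time 3 best (0.8039 against 0.804056). Difference in slopes = √[0.125 × (1/28 + 1/29)] = 0.0937, so the slopes are -0.0587 (control) and -0.1523 (test). Half the changes in the text, -0.12/2 and -0.31/2, agree closely.

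**Check 1: pooled error.** MSE = 5.75/55 = 0.1045.
- Test: SE = √(0.1045/29) = 0.0600, t = -2.54, p = 0.014.
- Control: SE = √(0.1045/28) = 0.0611, t = -0.96, p = 0.34.

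Over splits 27/30, 28/29, 29/28 and 31/26, with df 55 or n - 1, test p is 0.013 to 0.020 and control p is 0.28 to 0.37.

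**Check 2: arm-specific variances.** These must satisfy 27·s_A² + 28·s_X² = 5.75.
- If control p = 0.028, then t = 2.322 and s_A = 0.0587 × √28/2.322 = 0.134. So s_X = 0.434, test t = -1.89, p = 0.069.
- If test p = 0.001, then t = 3.674 and s_X = 0.1523 × √29/3.674 = 0.223. So s_A = 0.402, control t = -0.77, p = 0.45. A smaller test p makes the control p larger still.

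With slopes from the text means, the two results are 0.064 and 0.43. The stated pair cannot both be t-tests on these slopes.

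**Check 3: published SEMs, without Table 2.** The SE of a paired change is √(a² + b² - 2rab), which is at least |a - b|. Test arm: 0.166 - 0.071 = 0.095, reached only at r = 1. So t is at most 0.31/0.095 = 3.26 and p is at least 0.0029 on 28 df. With all rounding in the report's favour, t = 0.32/0.094 = 3.40 and p = 0.0020. At r = 0.5, test p = 0.040 and control p = 0.31. Control p = 0.028 needs r of about 0.95.

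**Between-arm figure.** (2.64 - 2.37)/√(0.130² + 0.166²) = 1.28, close to the stated t = 1.27. On 55 df, t = 1.27 gives p = 0.21. The printed 0.28 equals the Table 2 slope p-value.

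**Zeros.** Minimum slope -1.47 × 2 = -2.94, which is what a baseline of 2.94 recorded as 0 at Day 90 would give. Gingivitis and plaque also have minimum 0 at times 2 and 3. Assuming 29 test patients, the final SD is 0.166 × √29 = 0.894. Removing one, two or three zeros leaves SDs of 0.78, 0.63 or 0.378; four is arithmetically impossible. The baseline SD is 0.071 × √29 = 0.382, so three zeros would fit. This is an inference from an assumed n.

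**The case against.** The strongest reply is that the within-arm test is unnamed and need not be a t-test. The report says many distributions were far from normal. The largest slope is only +0.015, so almost no patient rose, and a signed-rank test could well give p < 0.001. A different patient set could too. This stands: a calculation error is not proven. A gamma model, however, cannot take zeros as they stand.

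Second, Table 2's error SS alone does not exclude test p < 0.001, because the variance could be divided unequally between arms. That also stands. For a t-test, the exclusion comes from the published SEMs and, separately, from the stated control p.

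Third, the site-level statement under Implants and Probing depth is a different analysis. It supports the point but does not directly contradict the global result.

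Fourth, the Conclusions claim an advantage only for plaque and gingival index, and the GPD section itself finds no treatment-by-time interaction. This limits the consequence but leaves the contradiction in place.

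Two stronger readings are tempting. One is that the true test-arm p is about 0.07. That figure trusts the control p of 0.028 and assumes it came from a t-test; pooled error gives 0.014. A single control zero from even the lowest baseline (2.04, slope -1.02) would force a control SD of at least √[(0.961² × 28/27)/27] = 0.188, where 0.961 is its distance from the control mean. That exceeds the 0.134 that 0.07 requires. The other is that the real fall was 0.04 mm, from 2.37 × 29/26 = 2.64 against 2.68. It assumes three zeros and compares 26 presumed follow-up values with the baseline of all 29, so it is not a paired change.

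**Conclusion.** The point holds. The GPD text and the Figure 3 caption contradict each other on one score. By t-test, the stated within-arm p-values do not follow from the published figures: test p is at least about 0.002 from the SEMs, and the stated pair is incompatible with Table 2. The SEM bound assumes that both SEMs describe the same patients. The pooled results (test 0.014, control 0.34) assume equal arm variances and the inferred split.

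A reader might infer that the caption is therefore right. The documents do not support that for the test arm, where the pooled fall is nominally significant; for control, the text's claim is the one that fails. All these figures include the Day 90 zeros, so they test the report's consistency and do not estimate the effect. That the zeros are missed visits is likely but unconfirmed. The between-arm slip (0.21 for 0.28) does not change the conclusion of no difference.

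**What to change.** 1. Check every Day 14 and Day 90 zero against the patient workbooks, set unobserved values to missing, and state how many there were in each arm.
2. Name the within-arm test and the patient set, with n per arm.
3. Recompute the change in global probing depth per arm on observed pairs, with SE and 95% CI.
4. Correct the p-value attached to t = 1.27, or label 0.28 as the Table 2 slope test; re-run both if the data change.
5. Keep the statements that depth fell significantly, and that both rinses reduced it similarly, only if the re-run supports them. Make the text and Figure 3 caption agree, and say that the site-level statement is a separate analysis.

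The cost is a short data check and re-run, with edits to one paragraph and one caption. A statement of within-arm benefit may be lost. The Table 2 probing-depth slope test would need re-running if zeros are removed.
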